4. OUTCOMES

Primary outcome

- Prevalence of middle-aged women with urinary incontinence.

Secondary outcomes

- Description of UI and related predictors, quality of life, social impact and costs.
- Association between UI and related predictors, quality of life, social impact and costs.

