UI prevalence and symptomatology	Lifestyle factors	
 Unhealthy voiding behavior (Hu and Pierre, 2019) and low physical activity may contribute to UUI onset (Li et al., 2023) Smoking cessation is a general public health measure and has been shown to be weakly associated with improving urgency, frequency and UI (Danforth et al., 2006; Harding et al., 2023) Decrease in fluid intake may improve some symptoms in patients with SUI and idiopathic detrusor overactivity (Swithinbank et al., 2005) Reduction of caffeine intake may reduce symptoms of frequency and urgency (Harding et al., 2023) An association was seen between alcohol consumption and urinary incontinence in middle-aged and older women (Lee & Hirayama, 2012)
	Frequency of urine leakage	To assess the severity of UI among female, we need measuring the “frequency” and “usual amount” of leakage ranged from “moderate” to “strong” (Avery et al., 2004)
	Perceived quantity of urine leakage	
	Type of urine leakage	It is focused on subtypes of urinary incontinence (SUI, UUI and MUI) (Abrams et al., 2003)
	Time of onset of urine leakage	The mean age in which urine leakage begins seems to be lower for SUI compared to MUI and UUI (Thangarajah et al., 2020)

 
I.R.C.C.S. Ospedale San Raffaele
	
STUDY PROTOCOL
	
WUIPS Version n. 1 23.08.2023

---	------------------------------	---

UI quality of life, social impact	General interference with daily life	The measurement of UI should incorporate the impact that the condition may have on quality of life (Avery et al., 2004)
	Interference with specifical activities	
Specifically:
 
 • Physical Activity • Social Relationships • Travel • Emotional Health 
(Monticone et al., 2021; Shumaker et al., 1994)

	Interference with sexual life	Some articles report that UI affects sexual aspects of the individual (Felsted & Supiano, 2019; Marques et al., 2015). According to other studies, sexual activity does not seem to be damaged by UI (Siracusano et al., 2003)
Costs	Work productivity	UI imposes a high economic burden because of work productivity loss (Goren et al., 2014)
	Weekly costs of hygiene care products	UI is associated with substantial routine care “costs” (Subak et al., 2006)

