9.1.1 UI Survey

A survey, written in Italian by the authors, will collect women's socio-demographic, economic and clinical characteristics, based on the variables reported in Table 1. The entire survey is attached in Appendix.

 
I.R.C.C.S. Ospedale San Raffaele
	
STUDY PROTOCOL
	
WUIPS Version n. 1 23.08.2023

---	------------------------------	---

A total of 29 questions will attempt to acquire information about some of the previously defined variables: specifically, 23 questions will be related to socio-demographic and clinical predictors of UI (n. 1-23), one question will be about the onset of the UI symptomatology (n. 35), one question about sexuality (n. 36) and four questions will investigate the direct and indirect costs of UI (n. 37-40). The survey was tested as a pilot on a sample of 13 women aged between 40 and 65 years old and was assessed as suitable for the following aspects: understanding and clarity of the questions, absence of questions that put the participant in difficulty, completion time (which resulted maximum of 5 minutes).

9.1.2 International Consultation of Incontinence Modular Questionnaire Urinary Incontinence Short Form (ICIQ UI-SF)

The International Consultation of Incontinence Modular Questionnaire Urinary Incontinence Short Form (ICIQ UI-SF) is a questionnaire that allows the assessment of the prevalence, frequency, and perceived cause of UI and its impact on everyday life. It is an appropriate scale for estimating national prevalence in representative samples (Bedretdinova et al., 2015).

ICIQ UI-SF was developed and validated in English for the first time by Avery and colleagues in 2004, and then Tubaro and colleagues made an Italian Validation in 2006. This last version will be used in the study.

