11. NUMBER OF CASES

The population sample cannot be decided accurately in advance. Population studies from numerous countries have reported that the prevalence of UI among all adult women ranged from approximately 5% to 70% worldwide, with most studies reporting a prevalence of UI in the range of 25–45% (Miano et al., 2012; Milsom & Gyhagen, 2019). To date, limited epidemiologic research has been conducted in Italy on this matter. One of the most recent Italian studies was conducted in 2002 and prevalence of UI was found to be 10.2% in a sample of 13365 women older than 40 years (Miano et al., 2012; Parazzini, Lavezzari & Arbitani, 2002).

To define an indicative sample size for our search, reference will be made to the sample considered by two prevalence studies conducted in some specifical Italian districts. The first one proposed telephonic interviews to the population of a big area composed by six cities, including a total of 2.767 women aged ≥ 40 years old (Bortolotti et al., 2000). The second study investigated by questionnaire the prevalence and characteristics of UI in a female sample composed by 2.900 subjects aged between 18 and 49 years living in the urban area of Trieste (Siracusano et al., 2003).

Our study will investigate UI prevalence in middle-aged women (40-65 years old) identified in four hospitals in Northern Italy. The competent Departments were asked for data on the average daily accesses of patients to the hospitals involved and the number of female personnel hired with an age range of 40-65

years. As regards the female personnel between 40 and 65 years old hired at San Raffaele Hospital and San Raffaele Turro Hospital, there are 1.842 employees. The sample will be determined based on the data we will receive from other hospitals.

After this study, we could expand the protocol to include other centers to better evaluate the phenomenon and investigate the prevalence in a larger population.

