16. Quanti parto cesarei ha avuto?

- 0
- 1
- 2

□ > 3

17. Pratica attività fisica in maniera frequente?

18. Fuma o ha mai fumato?

1. Attuale fumatore 2. Ex fumatore 3. Mai fumatore

19. Se fuma o fumava, quante sigarette al giorno consuma/consumava?

1-5 > 10-20
 > 5-10 > 20

20. Quanti caffè assume in media al giorno?

0 2
 1 3

21. Quanti drinks alcolici assume in media a settimana?

 0	 15-21
 1-7	 ≥ 22
 8-14	

22. Quanta acqua beve in media al giorno?

- 1. Meno di $\frac{1}{2}$ litro
- 2. Tra $\frac{1}{2}$ litro e un litro
- 3. Più di un litro, fino a un litro e $\frac{1}{2}$
- 4. Più di un litro e $\frac{1}{2}$

23. Quante volte al giorno svuota la vescica mediamente?

- 1. Ogni ora o più frequentemente
- 2. Ogni due-tre ore circa
- 3. Ogni quattro ore o meno frequentemente

ICIQ-UI Short Form (Italian)

A molte persone capita, a volte, di avere delle perdite di urina. Stiamo tentando di determinare quante persone abbiano delle perdite di urina e quanto ciò costituisca, per loro, un problema. Le saremmo grati se rispondesse alle seguenti domande facendo riferimento a come si è sentita, in media, nelle ULTIME QUATTRO SETTIMANE.

24. Con quale frequenza le capita di avere delle perdite di urina? (faccia una crocetta su una sola casella)

- 1. Mai
- 2. Una volta la settimana o meno
- 3. Due tre volte la settimana

- 4. Circa una volta al giorno
- 5. Più volte al giorno
- 6. Continuamente

25. Ci piacerebbe sapere qual è, secondo lei, la quantità di urina che perde. Quanta urina le capita di perdere di solito (sia quando indossa una protezione che quando non la indossa)? (faccia una crocetta su una sola casella)

- 1. Per niente
- 2. Una piccola quantità
- 3. Una discreta quantità
- 4. Una notevole quantità

26. In generale, in che misura le perdite di urina hanno interferito con la sua vita quotidiana? La preghiamo di fare un cerchietto attorno ad un numero tra 0 (per niente) e 10 (moltissimo)

0 1 2 3 4 5 6 7 8 9 10

per niente

moltissimo

27. In che occasione le capita di avere delle perdite di urina? (Indichi, tra le seguenti, tutte le situazioni che corrispondono al suo caso)

- 1. Mai – non ho perdite di urina
- 2. Ho perdite di urina prima di riuscire a raggiungere il bagno
- 3. Ho perdite di urina in occasione di colpi di tosse o starnuti
- 4. Ho perdite di urina quando sono addormentata

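### The only alcohol question does not define a drink and has no box between 0 and 1 a week, so exposure is likely to be misclassified, with bias of unknown direction and size

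*Protocol*

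**What the plan says.** Question 21 in the protocol's Appendix asks "21. Quanti drinks alcolici assume in media a settimana" and offers the boxes 0, 1-7, 8-14, 15-21 and 22 or more. It is the only alcohol item on the form. No section of the protocol defines a drink by beverage, volume or standard unit.

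Table 1 in Section 9 explains why alcohol is collected, as one of the lifestyle factors: "An association was seen between alcohol consumption and urinary incontinence in middle-aged and older women". The item serves a secondary outcome in Section 4: "Association between UI and related predictors, quality of life, social impact and costs". The primary outcome, prevalence, does not use it.

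Section 9.1.1 reports that the survey was piloted on 13 women aged 40 to 65 and found suitable in respect of "understanding and clarity of the questions, absence of questions that put the participant in difficulty", and of completion time. Sections 8 and 16 say that data are collected anonymously, on paper for patients and caregivers and in RedCap for staff.

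**The concern.** The item leaves two decisions to the respondent. The first is the unit: the Italian text uses the loan word *drinks* without saying whether a glass of wine with a meal, a beer or a small spirit each counts as one. The second is where to put an average below one per week, for which there is no box.

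Both decisions are made when the box is ticked. Section 16 says that records cannot be attributed to individuals. Section 16.1 mentions an identification number in a register, but no section provides for going back to a respondent. An analyst cannot later find out what a woman counted, or separate never from less than weekly. This is therefore a matter for the form and cannot be left to an analysis plan.

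Any result on alcohol as a predictor rests on this one line. If exposure is misclassified, the estimated association with UI may be wrong.

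**Working it through.** **Comparison with other items on the same form.** Question 22 (water) states a unit, the litre, and its lowest box is an open band below half a litre. Question 24 (leakage frequency) separates never from once a week or less. Question 38 (spending on products) gives examples in brackets and separates buying nothing from spending under 3 euros. Question 21 has no unit, no examples and no low non-zero band.

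**Is there a figure to reproduce?** No. The protocol states no effect size, power or sample size for the alcohol association. The arithmetic below only shows which way the bias can go.

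**Inputs.**
- UI risk in non-drinkers, p0: not given. As stand-ins I use the prevalences in Section 11: "with most studies reporting a prevalence of UI in the range of 25–45" per cent, and the Italian study in which "prevalence of UI was found to be 10.2% in a sample of 13365 women older than 40 years". So p0 = 0.102, 0.25 or 0.45.
- True odds ratio (OR), share f of women in the wrong box, and risk of occasional drinkers: all assumed.

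**Formulas.** Odds = p/(1−p). Risk in drinkers: p1 = odds(p0)·OR / (1 + odds(p0)·OR). Risk in a mixed box: (1−f)·p(main group) + f·p(misplaced group). Observed OR = ratio of the two observed odds.

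**Case A: women wrongly in the 0 box carry the full drinker risk.** With p0 = 0.25, OR = 1.5 and f = 20%: drinker odds = 0.3333 × 1.5 = 0.5, so p1 = 0.3333. The 0 box has risk 0.8 × 0.25 + 0.2 × 0.3333 = 0.2667, odds 0.3636. Observed OR = 0.5/0.3636 = 1.375. Across the three values of p0:

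| Share f of the 0 box | True OR 1.5 seen as | True OR 2.0 seen as |
|---|---|---|
| 10% | 1.43–1.44 | 1.83–1.87 |
| 20% | 1.37–1.38 | 1.69–1.74 |
| 40% | 1.26–1.28 | 1.45–1.52 |

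The bias is towards the null.

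**Case B: less-than-weekly drinkers tick 0 and have their own risk.** True OR for regular drinkers 1.5, f = 20% or 40%, p0 = 0.25 or 0.45.
- Same risk as abstainers (OR 1.0): observed OR stays 1.50.
- Slightly higher risk (OR 1.1): 1.44–1.47.
- Lower risk (OR 0.8): 1.57–1.64, away from the null. Example with p0 = 0.25 and f = 20%: occasional-drinker odds = 0.3333 × 0.8 = 0.2667, risk 0.2105; 0-box risk = 0.8 × 0.25 + 0.2 × 0.2105 = 0.2421, odds 0.3194; 0.5/0.3194 = 1.565.

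**Case C: undercounting moves women down one box.** Assumed true shares 40/40/20% in 0, 1-7 and 8-14, true ORs 1, 1.1 and 1.8, p0 = 0.25. If 10%, 20% or 40% of each drinking group moves down one box, the OR for 1-7 versus 0 *rises* from 1.10 to 1.12, 1.15 or 1.22. The OR for 8-14 versus 0 falls from 1.80 to 1.78, 1.77 or 1.75. The two bands are biased in opposite directions.

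**Case D: occasional drinkers with abstainer risk round up to 1-7.** With p0 = 0.25 and true OR 1.5, a 20% share gives a 1-7 risk of 0.8 × 0.3333 + 0.2 × 0.25 = 0.3167, odds 0.4634, observed OR 0.4634/0.3333 = 1.39. A 40% share gives 1.29. This is dilution, but through the 1-7 box, with the 0 box left clean.

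**The case against.** The strongest case against runs as follows. The survey was piloted in the target age group and judged clear, and that is the only evidence on clarity in the document. For a question about a weekly average, 0 is the nearest whole number for a woman well below one drink a week, so her measured amount is wrong by less than one drink. Alcohol is one topic among 23 predictor questions, it serves a secondary outcome, and five ordered bands may suit a graded analysis better than a drinker versus non-drinker contrast, which the protocol nowhere sets.

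Much of this stands as a limit on importance. It does not remove the defect. A woman can find the word *drinks* perfectly clear and still count differently from the next; the pilot description does not say whether the 13 women counted the same beverages. The small-error argument covers only the missing low box, not the missing unit, which affects every band.

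A reader might go further and infer that occasional drinkers, and women who leave out wine or beer, fall into the 0 group and so dilute the association. The documents do not support that. Nothing shows whether occasional drinkers tick 0 or 1-7, nothing shows that women leave out wine or beer, and an undercounting woman may land in a lower non-zero box. A reader might also scale the effect by the rule that the observed difference equals (1−x) times the true one, so that an assumed 7 points becomes 7 × 0.8 = 5.6 when 20% of the 0 box are drinkers. That rule gives the full drinker risk to every misplaced woman, including those with almost no exposure, and no figure for x exists in the protocol. Likewise, staff answer online and patients and caregivers on paper, so their reading of the word could differ, but nothing shows that it does.

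**Conclusion.** The point holds as a minor improvement to the form. It is certain from the document that question 21 defines no drink, has no box between 0 and 1 per week and is the only alcohol item. It follows that respondents set their own unit and that occasional drinkers may go to either of two boxes. Misclassification is therefore likely, and it cannot be repaired from anonymous forms.

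The consequence for the alcohol–UI association is a possible bias, often but not necessarily towards the null. Cases A and D dilute it, case B can leave it unchanged or strengthen it, and case C moves two bands in opposite directions. In cases A, B and D a true OR of 1.5 appears as anything from about 1.26 to 1.64. That span reflects the chosen assumptions and does not estimate the bias in this study, which the documents do not allow. The primary prevalence estimate is not touched.

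**What to change.** Before the form is first used, change question 21 in both the paper module and RedCap:
- State what counts as one drink, with examples and serving sizes for wine, beer and spirits. Beverage names without serving sizes would still leave the unit open.
- Replace the box 0 by two boxes, *mai* and *meno di una a settimana*. Keep 1-7, 8-14, 15-21 and 22 or more.

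The cost is a slightly longer item, one extra box, and notification of the revised form to the Ethics Committee, since Section 14 has new protocol versions shared with it. The reworded item will also differ from the one piloted, so a short check with a few women on what they counted would be sensible.

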9.1 Instruments

Three instruments will be employed to collect data, as reported in Table 2.

 I.R.C.C.S. Ospedale San Raffaele	STUDY PROTOCOL	WUIPS Version n. 1 23.08.2023
--	-----------------------	--

Table 2 - Instruments employed in the study

Instrument	Data of interests
UI Survey	Women's socio-demographic and clinical characteristics based on the variables reported in Table 1
Italian version of the International Consultation of Incontinence Modular Questionnaire Urinary Incontinence Short Form (ICIQ UI-SF) (Tubaro et al., 2006)	Prevalence and symptomatology of UI (Bedretdinova et al., 2015)
Italian version of the Incontinence Impact Questionnaire-7 (IIQ-7) (Monticone et al., 2020)	Impact on life of urinary incontinence among women (Shumaker et al., 1994)

A survey, written in Italian by the authors and tested on a sample of 13 women between 40 and 65 years old, will collect socio-demographic, economic and clinical characteristics of all the female participants included in the study. The requested data will be based on the variables reported in Table 1.

The Italian version of the International Consultation of Incontinence Modular Questionnaire Urinary Incontinence Short Form (ICIQ UI-SF) will be used to investigate UI symptoms in women (Avery et al., 2004; Tubaro et al., 2006).

The Italian version of the Incontinence Impact Questionnaire-7 will be used to assess the impact of UI on women's quality of life (Monticone et al., 2021; Shumaker et al., 1994).

The materials necessary for data collection will be included in a paper module for patients and caregivers and online for staff (see attachment). Each subject included will fill in the module which will be transmitted to the Promoter with the appropriately anonymized data. Given the growing need for digital data management in clinical trials and in compliance with current regulatory requirements, researchers will independently set up the eCRF (electronic Case Report Form), via the RedCap platform.

In each hospital center involved in the study, a nurse will be identified, as the contact person of the Center, who will be responsible for supervising the appropriate recording of data and compliance with this research protocol.

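### Survey question 23 records only voiding frequency, asks for a count but offers intervals, and has no clearly fitting option between about one and two hours

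*Protocol*

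**What the plan says.** Protocol section 9, Table 1, under lifestyle factors: "Unhealthy voiding behavior (Hu and Pierre, 2019) and low physical activity may contribute to UUI onset". The table does not say which behaviours are meant.

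Section 9.1 ties the survey to that table: "The requested data will be based on the variables reported in Table 1". Section 9.1.1 allocates the items: "23 questions will be related to socio-demographic and clinical predictors of UI (n. 1-23"). The same section adds that the survey tries to cover some of the listed variables, so it does not promise all of them.

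Appendix, UI Survey, question 23 has the stem "23. Quante volte al giorno svuota la vescica mediamente" and three options:
- "1. Ogni ora o più frequentemente"
- "2. Ogni due-tre ore circa"
- "3. Ogni quattro ore o meno frequentemente"

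No other predictor question concerns voiding. The neighbouring questions 20 to 22 ask about coffee, alcohol and water. Questions 24 to 27 concern leakage, 28 to 34 its impact, and 35 to 40 onset, sexual life, work and costs.

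**The concern.** Three features of question 23 do not fit its purpose.

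- **Content.** Table 1 names a behaviour; the item records how often the bladder is emptied. Table 1 itself treats frequency as a symptom: the entries on smoking cessation and caffeine list it beside urgency as something that may improve. An association between question 23 and UI could therefore reflect the condition as much as a habit that precedes it.
- **Stem against options.** The stem asks for a number per day; the answers are time intervals. Each respondent must convert, and the item does not say whether the night counts.
- **Coverage.** The options leave out intervals between one and two hours and, read literally, between three and four.

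Identifying predictors is a stated aim (sections 4 and 5). The data are collected anonymously (sections 8 and 16), so respondents cannot be asked again, and no analysis can recover a count that was collapsed into three ill-fitting boxes.

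**Working it through.** The protocol states no figure on this point, so there is nothing to reproduce. The check turns the interval options into daily counts.

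**Inputs from the Appendix, question 23.** Option 1: interval of 1 h or less. Option 2: about 2 to 3 h. Option 3: 4 h or more.

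**Assumption.** The hours H over which voids are counted are not given. I take 16 waking hours as the central case and show 14 to 18 h, and 24 h because the stem says per day.

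**Formula.** Voids per day = H / interval; interval = H / voids.

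**Central case, H = 16.**
- Option 1: 16 / 1 = 16 or more voids.
- Option 2: 16 / 3 = 5.3 to 16 / 2 = 8 voids.
- Option 3: 16 / 4 = 4 or fewer voids.
- Whole counts with an interval strictly between 1 and 2 h: 9 (960 / 9 = 107 min) to 15 (960 / 15 = 64 min).
- Whole counts with an interval strictly between 3 and 4 h: only 5 (16 / 5 = 3.2 h).

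**Lenient reading.** Option 2 contains 'circa' (about). If that stretches it to 1.5 to 3.5 h, its upper count at H = 16 becomes 16 / 1.5 = 10.7. Nine and ten voids (107 and 96 min) then fit option 2, and 11 to 15 remain uncovered. Five voids (3.2 h) also fit.

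**Range over H.**

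| H (hours) | Option 2, literal (voids) | 1–2 h gap, literal | 1–2 h gap, lenient | 3–4 h gap, literal | 3–4 h gap, lenient |
|---|---|---|---|---|---|
| 14 | 4.7–7 | 8–13 | 10–13 | 4 | none |
| 15 | 5–7.5 | 8–14 | 11–14 | 4 | 4 |
| 16 | 5.3–8 | 9–15 | 11–15 | 5 | none |
| 17 | 5.7–8.5 | 9–16 | 12–16 | 5 | none |
| 18 | 6–9 | 10–17 | 13–17 | 5 | 5 |
| 24 | 8–12 | 13–23 | 17–23 | 7 | none |

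The gap above one hour is present in every row under both readings. The gap between three and four hours never holds more than one whole count, and it closes in four of the six rows under the lenient reading.

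**Comparison within the survey.** Question 22, on water intake, uses bands that meet without holes. Question 23 is out of line with it, which points to a drafting slip.

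**The case against.** The strongest reply is that Table 1 leaves the predictor undefined, that voiding frequency is one aspect of voiding behaviour, and that question 23 yields a three-level ordered variable which can be tabulated or modelled against UI. Section 9.1.1 claims coverage of only some Table 1 variables. This stands. A reader might infer that the predictor is not measured at all, or cannot be related to UI; the protocol does not support that. Habits such as holding on or straining are named nowhere in it, so their absence cannot be called a departure from a stated definition. The predictor is measured in part.

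A reader might also infer that women voiding 9 to 15 times a day have no box. That figure belongs to an assumed 16-hour day read literally. On a 24-hour day, 9 to 12 voids fall inside option 2, and at 16 hours 'circa' reasonably admits 9 and 10. What stands is that intervals from one hour to about one and a half fit no option on either reading, and those from there to two hours fit only by stretching option 2.

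It is tempting to add that the choice of box depends on how bothered a woman is by leakage, making the error differential. That is plausible, but nothing in the protocol shows it, and it gives no proportion of women in the gap.

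Finally, the survey was piloted on 13 women and judged clear (section 9.1.1). The pilot looked at understanding, comfort and completion time, and no check of whether the categories cover all answers is reported. If, as an assumption, 5% to 10% of women void at intervals in the gap, a sample of 13 contains none of them with probability 0.95^13 = 51% to 0.90^13 = 25%. A clean pilot is weak reassurance here.

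**Conclusion.** The point holds in limited form. Question 23 is the only item bearing on an undefined Table 1 predictor and captures only voiding frequency. Its stem and options do not match, and its bands leave a gap between about one and two hours that survives every day length and reading tried. The counts in that gap rest on the assumed day length; the interval gap does not.

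The result is misclassification among frequent voiders in one secondary predictor. Its effect on any association cannot be sized from the protocol. The gap between three and four hours is too small to matter. The primary outcome is unaffected, because section 9.1, Table 2 assigns prevalence to the ICIQ UI-SF. The point still deserves correction because it sits in the printed instrument and cannot be repaired at analysis.

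**What to change.** Before data collection starts:

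1. Reword question 23 as a number over a stated period, for example voids per 24 hours, or day and night as two numbers. Alternatively keep intervals, make the bands contiguous and ask in the stem for the usual interval. The number is preferable because it can be grouped later. A count restricted to waking hours would drop night voids, so the period should be chosen deliberately.
2. Name the Table 1 variable voiding frequency, so that an association with question 23 is not reported as an effect of voiding behaviour.
3. Optionally, if behaviour itself is of interest, define it in Table 1 and add a short item. Its content would be new and would need piloting, so it is not required to resolve this point.

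Steps 1 and 2 cost one reworded item in the paper module and in RedCap, one changed label, and a brief check that the new wording is understood.

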	Healthcare resource utilization: 1. Specialist visits 2. Treatments	Women with SUI/MUI consume significantly higher medical resources and incur higher costs to payers, compared to women without SUI/MUI (Datar et al., 2022)

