The questionnaire comprises four question items and the reference period for symptom assessment is the four weeks preceding the day that the questionnaire is administered. The total score for the ICIQ-SF is calculated as the sum of scores obtained from the frequency of urinary incontinence episodes (from 0 or 'never', increasing by 1 unit up to 5 or 'always'), perceived quantity of urine losses (0 or 'no loss', increasing by 2 units up to 6 or 'a large amount') and quality of life (from 0 or 'no interference' of urinary incontinence with life, increasing by 1 unit up to 10 or 'maximum interference'). The theoretical range of total score values is therefore 0-21. A higher score indicates greater impairment from incontinence. The fourth question is an unscored self-diagnostic item about the type of urine leakage (Tubaro et al., 2006).

The instrument has a GRADE A on the level of validation according to the International Consultation of Incontinence (ICI) grades of recommendation; this means that the questionnaire has good validity, reliability and responsiveness established with rigor in several data sets. Specifically, the internal consistency of the ICIQ-SF is satisfactory overall, with a Cronbach's α of 0.896. Also the test-retest reliability is good; the Pearson r coefficient is almost equal to 1 for the total score and varies steadily at ≈ 0.9 for all items. Intraclass correlation coefficients for the total score and the quality of life item are, respectively, 0.93 and 0.96 (Tubaro et al., 2006). The entire questionnaire is attached in the Appendix (questions n. 24-27).

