- 5. Ho perdite di urina quando sono in movimento e durante l'attività fisica
- 6. Ho perdite di urina quando ho finito di urinare e mi sono rivestita
- 7. Ho perdite di urina senza ragioni particolari
- 8. Ho perdite di urina continuamente

Incontinence Impact Questionnaire-7 (Italian)

Le saremmo grati se rispondesse a queste ultime domande, per comprendere l'influenza sulla qualità di vita delle perdite di urina che ha riscontrato.

NOTA BENE: Se non ha mai riscontrato perdite di urina, le chiediamo di apporre una crocetta sul seguente quadratino e di non rispondere alle domande nella tabella. Grazie per la collaborazione.

- Non ho perdite di urina

Se ha riscontrato perdite di urine, queste perdite hanno influenzato...

	Per nulla	Molto poco	Un po'	Molto
28. La sua capacità di fare le faccende domestiche (cucina, pulizie di casa, lavanderia, ecc.)?	0	1	2	3
29. Le sue attività fisiche ricreative, come camminare, nuotare, o fare	0	1	2	3

altro esercizio?				
30. Le sue attività del tempo libero (andare al cinema, concerti, ecc.)?	0	1	2	3
31. La sua capacità di viaggiare in auto o in autobus per più di 30 minuti da casa?	0	1	2	3
32. La sua partecipazione ad attività sociali fuori casa?	0	1	2	3
33. La sua salute emotiva (nervosismo, depressione, ecc.)?	0	1	2	3
34. I suoi sentimenti di frustrazione?	0	1	2	3

Di seguito le poniamo qualche domanda su insorgenza, evoluzione, impatto della patologia e costi da essa derivanti.

NOTA BENE: Se non ha mai riscontrato perdite di urina, le chiediamo di apporre una crocetta sul seguente quadratino e di non rispondere alle domande successive. Grazie per la collaborazione.

Non ho perdite di urina

35. Da quanto tempo ha delle perdite di urina?

- 1. Da 1 anno o meno
- 2. Da 2-5 anni
- 3. Da 6-10 anni
- 4. Da più di 10 anni

36. Le sue perdite di urina hanno influenzato la sua vita sessuale?

- 1. Per nulla
- 2. Molto poco
- 3. Un po'
- 4. Molto

37. Le sue perdite di urina hanno comportato assenteismo o minore produttività sul posto di lavoro?

- 1. No
- 2. Sì, raramente
- 3. Sì, a volte
- 4. Sì, spesso

38. In media, potrebbe fornire una stima della spesa settimanale che sostiene per l'acquisto di prodotti igienici specifici per le perdite di urina (assorbenti o pannolini, salviettine, detergenti intimi specifici, ecc.)?

- 1. Non acquisto alcun prodotto specifico per le perdite di urina
- 2. Spendono meno di 3 euro a settimana
- 3. Spendono fino a 5 euro a settimana

- 4. Spendò tra i 6 e i 10 euro a settimana

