- 5. Spendò più di 10 euro a settimana

39. Ha svolto delle visite specialistiche per il problema delle perdite di urina?

- 1. No (perché _____)
- 2. Sì, con un ginecologo / un urologo
- 3. Sì, con un'ostetrica / un infermiere / un fisioterapista
- 4. Sì, con un altro professionista sanitario (specificare _____)

40. Sta seguendo qualche trattamento per risolvere il problema delle perdite di urina?

- 1. Sì (specificare _____)
- 2. No

LA RINGRAZIAMO MOLTO PER AVER RISPOSTO ALLE NOSTRE DOMANDE

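### The stop box before question 35 contradicts its own instruction, so women now dry on treatment may skip the only questions on specialist visits and treatment

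*Protocol*

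**What the plan says.** Section 9, Table 1 of the Protocol lists "Healthcare resource utilization: 1. Specialist visits 2. Treatments" among the cost variables. In the Appendix this variable rests on two researcher-written items: question 39, "Ha svolto delle visite specialistiche per il problema delle perdite di urina", and question 40, "Sta seguendo qualche trattamento per risolvere il problema delle perdite di urina".

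Both follow a stop box placed before question 35, which asks the woman to tick and stop: "le chiediamo di apporre una crocetta sul seguente quadratino e di non rispondere alle domande successive". With its opening condition, the full instruction reads "Se non ha mai riscontrato perdite di urina, le chiediamo di apporre una crocetta sul seguente quadratino e di non rispondere alle domande successive": if you have never had leakage, tick and do not answer what follows. The label beside the box is "Non ho perdite di urina", that is, I have no leakage. The first question after the box is "Da quanto tempo ha delle perdite di urina", with four answers running from one year or less to more than ten years.

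Prevalence is taken from the ICIQ UI-SF (questions 24 to 27), which precedes the box. According to section 9.1.2, "the reference period for symptom assessment is the four weeks preceding the day that the questionnaire is administered".

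**The concern.** The instruction sorts women by whether they have ever leaked. The label sorts them by whether they leak now. The two criteria disagree for a woman who leaked in the past and is currently dry on treatment. If she goes by the label, her visits and her treatment go unrecorded.

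At stake is a named secondary variable. Section 2 gives projection of the need for health services as a purpose of a prevalence study, and women whose treatment works use those services. The loss happens at collection: an answer that was never given cannot be recovered in analysis, and because the data are collected anonymously (sections 8 and 16) a skipped answer is unlikely to be queried.

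**Working it through.** **Step 1. Follow one woman through the form.** She leaked earlier, is now treated without surgery, and has been dry for four weeks. Section 7.2 excludes women with urinary or gynecological surgery, so only non-surgical treatment is at issue.

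- Questions 1 to 23: none records treatment of, or visits for, leakage. The comorbidity list in question 8 does not name incontinence, and questions 9 and 10 concern surgery.
- Questions 24 to 27: she reports no leakage in the last four weeks. The first option of question 27 uses the same phrase as the later box label, here within the four-week frame.
- IIQ-7 box: the same combination of a never condition and a present-tense label appears.
- Box before question 35: the condition (never leaked) is false for her, while the label (no leakage) is true for her.
- Question 35, if she continues: it asks how long she has been leaking, and no answer fits.
- Questions 39 and 40: she reaches them only if she followed the condition and passed question 35.

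Her loss is therefore a risk created by ambiguous wording. It is not a certain result of the design.

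**Step 2. Illustrate the size.** The Protocol states no treated share, dry share or rate of ticking, so there is no figure to reproduce. Assumed inputs:

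- C, the share of women leaking now or dry on treatment: 10.2% to 45% (10.2% is the Italian figure in section 11; 45% is the top of the 25–45% range given there)
- t, the treated share of C: 5%, 15% or 30% (assumption)
- d, the dry share of the treated: 10% or 30% (assumption)
- s, the share of dry treated women who tick the box: 0, 0.5 or 1 (assumption)

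Treated share among those who answer question 40 = [C·t·(1−d) + C·t·d·(1−s)] / [C·(1−t·d) + C·t·d·(1−s)] = t(1−d·s) / (1−t·d·s). C cancels.

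Example with t = 0.15, d = 0.30, s = 1: 0.15 × 0.70 / (1 − 0.045) = 0.105 / 0.955 = 11.0%.

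| True t | d | s = 0 | s = 0.5 | s = 1 |
|---|---|---|---|---|
| 5% | 10% | 5.0% | 4.76% | 4.52% |
| 5% | 30% | 5.0% | 4.28% | 3.55% |
| 15% | 10% | 15.0% | 14.36% | 13.71% |
| 15% | 30% | 15.0% | 13.04% | 10.99% |
| 30% | 10% | 30.0% | 28.93% | 27.84% |
| 30% | 30% | 30.0% | 26.70% | 23.08% |

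The column s = 1 is the upper bound of the loss. At s = 0 nothing is lost.

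**Step 3. Check the primary outcome.** Four-week prevalence = C(1−t·d). It does not contain s, so the box cannot change it. The difference from C is C·t·d: from 0.102 × 0.05 × 0.10 = 0.05 points to 0.45 × 0.30 × 0.30 = 4.05 points. That is the distance between two definitions, current leakage versus current or controlled leakage.

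**Step 4. Check the comparison group.** Dry treated women form C·t·d / (1 − C + C·t·d) of the non-cases: from 0.051/89.851 = 0.06% to 4.05/59.05 = 6.9% over the same inputs.

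**The case against.** The strongest reply is that the printed condition is right. It limits the box to women who have never leaked, so a woman dry on treatment is sent on to questions 39 and 40. On that view only a label needs rewording, and aligning it with the instruction recovers the data (s = 0). This stands as far as it goes: nothing in the form tells her to stop. But the label and question 35 both point the other way. If the two were aligned in the other direction, on four weeks, the loss would become certain. Asking the two items of everyone works under either choice.

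A second reply is that section 5(d) describes costs of women with UI. If that means current leakers, the treated share among leakers is the correct figure and the box does it no harm. This also stands for that population. The instruction, however, admits women who leaked in the past, so the form seeks their answers and may receive only an unknown part of them.

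A reader might also infer that UI prevalence is understated. The documents do not support this. Section 1 defines UI by the complaint of leakage and the instrument asks about four weeks, so a dry woman is a correct non-case. A reader might infer that skipped women are recorded as untreated, or that treatment is captured only when it fails. A skipped item is blank, the Protocol does not say how blanks are coded, and treated women who still leak partly are recorded. Stronger masking among healthcare staff has no support in the text.

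**Conclusion.** The point holds as a defect of the form with a limited reach. Condition, label and first follow-up question do not agree, and the only two items on healthcare use for leakage lie behind them. Visit and treatment use may be understated among women with current or controlled leakage. The amount cannot be derived from the Protocol, because it depends on the treated share, the dry share and above all on how many women follow the label. The illustrated losses at s = 1 assume that every dry treated woman ticks the box against the instruction, and should be read as a bound. The primary four-week prevalence stands. This is a cheap improvement that protects a secondary variable.

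**What to change.** 1. Place questions 39 and 40 before the second stop box so that all participants answer them, in the paper module and in the online version. Let question 40 distinguish current, past and never. Both items are researcher-written, so the validated questionnaires are untouched.
2. Make the box label agree with its instruction.
3. Add a past or controlled leakage option at question 35.
4. Keep leakage in the last four weeks as the primary prevalence. Optionally, report leakage in the last four weeks or current treatment for it as a secondary descriptive figure, and run the association analysis with and without currently treated dry women in the reference group.

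Cost: two items moved, a few words changed, and extra answer options at questions 35 and 40. Continent women answer two more short questions.
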